## Experimental Procedure

1. Baseline evaluation of suicidal severity (BSSI) & degree of depressive symptoms (MADRS-S) will be evaluated through self-administered questionnaires.
2. The experimental and placebo arms will receive a single dose of IV ketamine, 0.5 mg/kg in 100 cc NS or 100 cc of NS infused over 40 minutes.
3. Post ketamine re-evaluation of outcome measures at four and twenty-four hours will determine clinical effectiveness of ketamine intervention
4. Inspection of admission and transfer time provides time measurement for LOS. This secondary measure is needed to determine efficiency of intervention.
5. Post ketamine re-evaluation of outcome measure at one-week post infusion will elucidate ketamine's durability of effect.

**Table 2:** Description of activities at time points during the study

|  | Study Visit 1
Baseline ( $t_0$ ) | Study Visit 1
4 hours ( $t_1$ ) | Study Visit 1
24 hours ( $t_2$ ) | Study Visit 2
1 week ( $t_3$ ) |
|--|-------------------------------------|------------------------------------|-------------------------------------|-----------------------------------|
|  |                                     |                                    |                                     |                                   |

|  |   |   |   |   |
|--|---|---|---|---|
| Eligibility review and confirmation                    | X |   |   |   |
| Education regarding research & Informed Consent signed | X |   |   |   |
| History & Physical                                     | X |   |   |   |
| Randomization  | X |   |   |   |
| Dispense study drug                                    | X |   |   |   |
| IV Ketamine  | X |   |   |   |
| Vital Signs & ADR* monitored                           | X | X | X |   |
| Review adverse events                                  | X | X | X |   |
| Psychometric testing                                   | X | X | X | X |

\*ADR: Adverse drug reaction

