#### RESEARCH DESIGN/METHODS/SUBJECT JUSTIFICATION

##### General Approach

This study will be conducted in the ED. The investigative team will notify the ED that this research is underway. Emergency Department staff will be given an informational brief regarding the nature, purpose and scope of the research protocol. The brief will be distributed digitally via email, and will be discussed in staff meetings and huddles to reach 100% of staff. Healthcare personnel who wish to participate will be given a script and check list for exclusion criteria. If a physician feels that a patient may be eligible for participation he/she can refer the patient to the research team for additional evaluation and approach regarding the research study." The role of this individual is only for recruitment purposes and will not be involved in any other activities of the protocol or informed of patient information pertaining to the research.

Participants will be adults, whom are 18 years or older, military personnel or civilians eligible for care in the military treatment facility. This study aims to test for a clinically significant decrease in SI in the acutely suicidal patient. Repeat measures over time will be conducted at two subsequent

time points. To determine week long lasting effects of treatment, a third repeat measure will be conducted. All time point collections will be done for both arms.

The trial is designed as a double-blinded Randomized Control Trial (RCT) with two arms, Experimental vs. Placebo. This trial will mask patients, health providers, and outcome assessors to avoid ascertainment bias; the only unblinded participants will be the pharmacy, which will not affect the blinding, because at our institution they do not decide on patient disposition. This study design is not only necessary to demonstrate the effectiveness as a treatment for the acutely suicidal patient, but also to validate and add power to studies supporting anti-suicidal properties of ketamine. Outcomes will be measured by Psychometric testing (BSSI & MADRS-S). With the exception of the aforementioned experimental procedure, which will be done prior to transfer to inpatient units, both arms will then be treated in accordance to usual management for suicidal patients, which for both arms includes inpatient admission, therapy, and possible initiation of antidepressants.

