Suicidal patients, subjectively identified by clinician, upon admission to the ED will be medically cleared by the EM physician, and then meet with the mental health liaison to be screened for admission to the psychiatric department, per normal standard of care. Study investigators will not be available around the clock, but when available will begin the pre-screening method for this investigation. The treating physician will pre-screen them for inclusion and exclusion criteria per an IRB approved check list (Appendix D: Criteria Checklist).

The patient will be approached for informed consent in accordance to with 21 CFR 50. They will be provided with a written document that embodies the elements of the informed consent. The consent will be presented orally to the subject with a witness. Once presented the subject will be given a reasonable time to review the contents and inquire information. Upon signing of the form, a copy shall be given to them.

Once consent is obtained, they will be presented with a paper form to complete the BSSI and MADRS-S. These measures will serve as baseline severity of suicidal wishes and plans, and degree of depression symptoms. Questionnaires will be stored in locked drawer's in the locked office the Division Officers in the Emergency Department, the Inpatient Mental Health ward, or the study coordinator.

Once the patient is deemed medically cleared by the treating physician, the study treatment will be ordered by an ED provider, per the randomization schedule, and administered by an ED nurse (Please see below for more detailed methodology). Those in the experimental arm will be treated with 0.5 mg/kg IV infusion of ketamine over 40 minutes. Those in the control arm will be treated with 100 cc Saline infusion over 40 minutes. (Table 1) Since there are no pharmaceutical treatment specific for acute suicide, it is in accordance to the Declaration of Helsinki (DOH) to utilize a saline placebo control. Vitals will be checked every 5 minutes during infusion. Questionnaires will be repeated at four time points for both arms, once in the ED before drug administration, one at 4 (+/-1) hours post-infusion, whether in the ED or the psychiatric unit, another 24-36 hours after the infusion in the inpatient psychiatric unit, and lastly one-week (+1 day) post treatment by phone call.

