#### Research Objective

The primary objective of this investigation is to identify utility of Ketamine as a clinically effective and efficient adjunctive treatment modality for the acutely suicidal patient in the ED setting. Secondary objective is to investigate prospectively if the anti-suicidal effects are able to have lasting effect up to one week within the vulnerable period post discharge.

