Finally, patients will perform psychometric tests, ideally, one-week post infusion. They will be called at their phone number on file. The follow up BSSI will be administered by a study evaluator. Forms will be filled out, placed in trial mailbox, data transferred onto spreadsheet.

*Potential difficulties:*

1. Continuation/Concomitant use of psychotropics influence the same neurotransmitter as ketamine, making it difficult to discern direct effects of ketamine.
2. Heterogeneity of patients, enhances generality, but reduces confidence in any conclusions drawn.
3. Difficulty lie inherently in treating those with mood instability and difficult-to-treat patients.
  - a.) Those with mood disorders (BD & MDD) may metabolize ketamine differently

*Potential limitations*

1. Sample size
2. Need for replication
3. Placebo effect
4. Enrollment is only available when eligible study personnel are present
5. Depression is a placebo-responsive illness. Because suicide risk varies with the nature of depressive or mood disorder, the placebo effect is uncertain. Increased placebo effect increases variance and poor signal detection.
6. Lack of translational studies, especially in neurobiology of suicide.
7. SI measures suicide risk. However, it does not measure other psychological constructs associated with increased suicidal risk, such as hopelessness.
8. Lack of variety of outcome measure limits the study.
9. There is no established clinical biomarker predictor of ketamine.

[figure not shown]

Figure 1: Flow of Experimental procedure

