#### ADVERSE EVENT MANAGEMENT AND REPORTING

Unanticipated problems involving risk to subject or others, serious and unexpected adverse experiences related to participation in the study and all subject deaths will be promptly reported in accordance with the requirements of the Naval Medical Center Camp Lejeune Institutional Review Board. The local site PI and/or overall study PI will report all serious adverse events (SAE) occurring among enrolled subjects to the NMCCIRB within 24 hours of the discovery of the adverse event. The PI will submit an internal adverse event report memorandum to the IRB. Unexpected (but not serious) adverse events occurring among enrolled subjects which, in the opinion of the local site PI or overall study PI, are possibly related to participation in the protocol, will be reported by the local site PI and/or overall study PI within 24 hours to the IRB using this same procedure. A summary of all adverse events will be submitted along with the annual continuing review report.

Serious adverse events will be addressed through standard emergency resuscitative care (Table 5) will be rendered. The IRB will be notified within 24 hours of any case of serious adverse events.

**Table 5:** Rapid overview for the management of ketamine intoxication

| Clinical presentation   |
|---|
| Impaired consciousness is the most common presentation, although ketamine intoxication may cause a range of central neurologic symptoms, from mild agitation to hallucinations; mild tachycardia and hypertension often occur |
| Massive overdose can cause coma or apnea  |
| Laryngospasm and heavy salivation may infrequently occur during intravenous use, even with standard doses; laryngospasm is rare but occurs most often in infants  |
| Vertical or rotatory nystagmus may occur  |
| Diagnostic testing  |
| Diagnosis of ketamine intoxication is based on history and clinical evidence; no readily available definitive laboratory test exists  |
| Obtain fingerstick glucose, acetaminophen and salicylate concentrations, electrocardiogram, and pregnancy test in women of childbearing age   |
| Management  |
| Secure airway, breathing, and circulation   |
| Laryngospasm and respiratory depression   |
| Generally, resolve with noninvasive support (e.g., bag-mask ventilation; oxygen); endotracheal intubation is rarely required  |
| Salivation that compromises respirations or interferes with procedures  |

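### Table 2 schedules no adverse-event review at the one-week contact, so events after the 24-36 h assessment are not systematically asked about

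*Combined protocol and SAP*

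**What the plan says.** Table 2 has four time points: baseline, 4 hours, 24 hours and one week. The row "Review adverse events" is marked at the first three only. The row for vital signs and adverse drug reactions has the same pattern. Psychometric testing is the only row marked at one week.

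The text agrees with the table. General Approach in Section 10.1 places the last two assessments as "another 24-36 hours after the infusion in the inpatient psychiatric unit, and lastly one-week (+1 day) post treatment by phone call". Methods and Materials describes the final contact in terms of questionnaires: "Finally, patients will perform psychometric tests, ideally, one-week post infusion", and "The follow up BSSI will be administered by a study evaluator". Section 9.3 also describes a phone call, but times it from the first questionnaire rather than from the infusion. Section 10.2 adds a separate authorisation for email at the one-week follow-up.

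On reporting, Section 16.1 requires serious adverse events in enrolled subjects to go to the IRB "within 24 hours of the discovery of the adverse event", and requires subject deaths to be reported promptly. Neither duty has an end date. The section also promises that "A summary of all adverse events will be submitted along with the annual continuing review report".

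**The concern.** A duty to report is not a method of finding events. The 24-hour clock in Section 16.1 starts at discovery, and nothing visible plans for discovery after the 24-36 h assessment. The annual summary can contain only what someone happened to learn.

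The interval matters in this population. Section 9.2 describes the days just after discharge from the ED or psychiatric unit as high risk, with the elevation lasting up to a month. The secondary objective looks for a "lasting effect up to one week within the vulnerable period post discharge". That is an efficacy objective measured by questionnaire, not a commitment to collect safety data, but it shows that the plan regards this week as clinically important. Section 14.4 also suggests that treatment may lower the risk of repeat attempts. Self-harm, attempts and readmissions are the events a reader of such a trial would want ascertained in the same way in both arms. The one-week scale measures severity of ideation and does not replace asking about them.

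**Working it through.** **Is the blank cell genuine?** Each row of Table 2 has four time cells, and the psychometric row is filled in all four. A blank in the fourth cell of the adverse-event row is therefore unlikely to be a text-extraction fault, and the narrative points the same way.

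**Is the inquiry scheduled elsewhere?**

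| Place | What it covers | Adverse-event inquiry after 24-36 h? |
|---|---|---|
| Section 9.3 | One-week phone call | No |
| Section 10.1, General Approach and Methods and Materials | Questionnaires at one week | No |
| Section 10.2, data list | Scales, history, medication, admission and transfer times | No adverse-event item |
| Table 3, data sheets | Identifier key, demographics, length of stay, BSSI, MADRS | No adverse-event sheet |
| Section 16.1 | Reporting and treatment of events | No; the form asks how unexpected events will be identified, and the answer does not say |

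**Length of the unscheduled interval.** Inputs from General Approach, timed from infusion: last assessment with a scheduled review at 24 to 36 h; one-week call at 7 × 24 = 168 h, or up to 168 + 24 = 192 h with the one-day window.

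- Shortest: 168 − 36 = 132 h, and 132 / 24 = 5.5 days.
- Longest: 192 − 24 = 168 h, and 168 / 24 = 7.0 days.

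For a call at exactly 168 h, the interval is 132 / 168 = 79% to (168 − 24) / 168 = 144 / 168 = 86% of follow-up.

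If the call is timed from the first questionnaire, as in Section 9.3, it comes earlier by the delay between questionnaire and infusion. Calling that delay x hours, the range becomes (132 − x) to (168 − x) hours. The plan gives no value for x. Since both steps take place in the same ED visit, the interval should be only slightly shorter.

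**What cannot be computed.** The plan gives no event rate, no inpatient length of stay and no phone non-response rate. It therefore supports no figure for missed events, for unsupervised days or for patients not reached.

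**The case against.** The strongest defence is that the schedule suits the drug. This is a single 40-minute infusion, and Section 14.1 expects dissociative symptoms to clear within 120 minutes, long before the 24-36 h review. That stands: acute drug effects are covered.

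There are also other routes by which later events may come to light. All patients are admitted under usual management, "which for both arms includes inpatient admission, therapy, and possible initiation of antidepressants", and Methods and Materials has the ED nurse tell the psychiatric unit that the patient is enrolled. The research monitor may interview subjects (Section 5.2). At one week a study evaluator speaks to the patient and could hear of an event. These routes reduce the weight of the point, but none is a scheduled inquiry made alike for every patient. Figure 1, the Appendix D data sheet and any monitoring plan under Section 15.1 are not visible and could contain such a check. If one does, Table 2 only needs to be brought into line with it.

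It is also fair that no analysis in Table 6 uses adverse events, so no planned efficacy result depends on this.

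Two stronger readings are tempting. A reader might infer that late serious events need not be reported; Section 16.1 says otherwise, because the duty has no end date. A reader might also take the 10% dropout allowance in Section 11.5 as a ceiling on patients missed at the call. That allowance is for overall dropout, which also has to absorb patients removed because the infusion was stopped. It is not a rate of phone non-response.

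**Conclusion.** The point holds as a gap in scheduled ascertainment, not in the duty to report. Followed as written, the schedule leaves self-harm, attempts, readmission and other events unasked about for about 5.5 to 7 days after the 24-36 h assessment, or slightly less if the call is timed from the first questionnaire. Part of that time is supervised inpatient care of unknown length.

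This rests on two assumptions: that the 24-hour review in Table 2 falls in the 24-36 h window, and that the unseen figure, appendix and monitoring plan add no one-week check. Confidence is medium for that second reason. It would go too far to say that events will be missed, or to state how many. The change is worth making because it is cheap and concerns a period the plan itself treats as high risk; it is not a threat to the primary comparison.

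**What to change.** 1. Mark the adverse-event review at one week in Table 2.
2. Have the study evaluator ask every patient, in both arms, one standard question covering self-harm, suicide attempts, readmission and any other adverse event since the last review. Record the answer, including a negative one, on the data sheet.
3. For patients not reached by phone, use the email contact for which Section 10.2 seeks authorisation. If that fails, check the electronic medical record, already listed as a data collection tool, for the same events and record the result. First confirm that the consent wording covers records made after the infusion, because Section 10.2 describes the consented access as medical history.

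The call, the evaluator and the record access are already in the plan. The cost is a few minutes per call, one row on the data sheet, a chart check for patients not reached, more events to report and a minor protocol amendment. Design, sample size and analysis do not change.

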## 10.2 Data Collection:

Describe all the data variables, information to be collected, the source of the data, and how the data will be operationally measured.

### Research Material to Be Collected

1. The protocol requires patients to submit the following data:
  1. Phone number and email
  2. To measure SI severity, Self-administered BSSI (Appendix D: Sample BSSI)
  3. Level of depression shall be measured by the self-administered version of Montgomery-Åsberg Depression scale (MADRS-S). (Appendix D: MADRS-S)
2. The following information are obtained per standard of care, and will be collected through chart review:
  1. Medical history
    1. Psychiatric history
    2. Current and or Previous Diagnoses
    3. Current/recent antidepressant medication
    4. Current psychotropic medications
  2. Time stamps (admission & transfer)
3. The following additional information will be collected
  1. Class: military or civilian
  2. Number of previous suicide attempts
  3. History of self-harm
  4. Recent use of antidepressants
  5. Any applicable ancillary studies such as labs or imaging modalities
  6. Appendix D: Sample Data Collection Sheet
4. Identifier will be maintained in a spreadsheet that correlates subject identifier number and subject name. This will exist in privileged shared folder that only Investigators have permission to access. Data sheets will be coded such that only subject identifier numbers will exist on them.
5. Waiver of Authorization for the Use of PHI will not be necessary because request for access of medical history for research purposes is a component of the consent document. A separate authorization for the use of email in the one week follow up will also be requested at the time of consent.

### Data Collection Tools

1. Pearson's BSSI paper form
2. MADRS-SI paper form
3. EMR for chart review
4. Excel for data sheets

**10.3 At any point in the study, will you request, use, or access health information in any form, including verbal, hard copy and electronic?**

Yes  No

**10.4 Review the definitions below and respond to the following two questions. If you are not sure of the answers, email [contact] for assistance. The *Military Health System (MHS)* is defined as all DoD health plans and DoD health care providers that are organized under the management authority of, or in the case of covered individual providers, assigned to or employed by, the Defense Health Agency (DHA), the Army, the Navy, or the Air Force. *MHS workforce members* are employees, volunteers, trainees, and other persons whose conduct, in the performance of work for the MHS, is under the direct control of the MHS, whether or not they are paid by the MHS. *MHS business associates* are persons or entities that provide a service to the MHS and require protected health information (PHI) to provide the service.**

**Are you an MHS workforce member?**

Yes, I am an MHS workforce member  
 No, I am not an MHS workforce member

**Are you an MHS business associate?**

Yes, I am an MHS business associate  
 No, I am not an MHS business associate

**10.5 Have you consulted with an MHS data expert to determine the data elements required for your study?**

Consulting with a data expert often saves time later in the compliance process because the data expert can advise on the data available in the numerous MHS information systems, the quality of that data and the methods for encrypting and collapsing data. To schedule a consult with an MHS data expert, send an email to: (**[contact]**)

Yes, then complete the questions below according to the data consult  
 No, then complete the questions below according to the best of your knowledge

**10.6 Indicate how you will request data from the MHS. Select all that apply.**

Talking with MHS health care providers or MHS health plans about specific research participants  
 Obtaining MHS hard copy records specific to research participants  
 Obtaining data from an MHS information system(s)

**10.7 If you are obtaining data from an MHS information system(s), indicate whether you plan to receive a data extract or whether you plan to access an MHS information system directly to create a data set.**

A data extract is when the MHS or a contractor provides the data set directly to the researcher. When receiving a data set through data extract, the researcher may indicate whether the data elements should be provided as is, encrypted or collapsed. In contrast to a data extract, access to an information system means that the researcher may directly access an MHS information system and create a data set for the research study

Data Extract  
 Access

**10.8 Do you intend to request de-identified data from the MHS in your research study?**

There are different two methods for de-identifying data pursuant to HIPAA:

1) Safe Harbor Method: Removing all of the identifiers listed in Table 1 below, provided that the researcher does not have actual knowledge that the remaining data can be used alone or in combination with other information to identify the individual who is the subject of the information

2) Statistical Method: An expert, with appropriate knowledge of and experience with generally accepted statistical and scientific principles and methods for rendering information not individually identifiable, determines that the data is not individually identifiable

Yes  No

